9.4 Safety Variables

Safety will be evaluated by tabulations of adverse events and will be presented with descriptive statistics at each visit for each treatment group. The statistical evaluations will be organized by Treatment Phase (Weeks 0-16) and Crossover/Open-label phase (16-52). The number and percentage of subjects experiencing an AE/SAE will be stratified by system organ class, or a preferred term, and severity of the adverse event, and recorded and tabulated overall by each sub-strata. Each subject will be counted only once within a system organ class or a preferred term using the adverse events with the highest severity within each category. All information pertaining to adverse events noted during the study will be listed by subject, detailing verbatim given by the investigator, preferred term, system organ class, date of onset, date of resolution, severity, and relationship to treatment. A tabulation of Serious Adverse Events (SAEs), will be provided by subject within treatment groups. The proportion of subjects in each treatment group reporting adverse events that occur in ~ 5% in either treatment group will be compared using the Fisher's exact test.

The specific system organ classes and preferred terms analyzed will be those that are reported by at least five percent of the subjects in either treatment group.

9.5. Sample size Justification:

Sample size estimation for this trial is based on the comparison of the change in the composite IASI score from baseline to 16 weeks post treatment between the secukinumab and placebo arms. Data from our cohort

Product: Secukinumab

Protocol Number: CAIN457AUS05T

Date: 14 July 2018

36

of 21 adolescents and adults was used to estimate the sample size. The mean composite IASI score in this cohort was 28.9 with a standard deviation of 9.0. Assuming a correlation between the pre and post treatment IASI scores of 0.55, we estimated the standard deviation of the baseline to week 16 change at approximately 8.5. Fixing the type I error at 0.05 for a two tailed t-test, a sample size of 16 subjects per group provides 80% power to detect a treatment effect of 30% for change in the IASI composite score (40% reduction in the secukinumab vs. an 10% reduction in the placebo arm). To account for an anticipated 20% dropout rate, 20 subjects in each treatment group (total 40) will be randomized.

9.6. Analysis of Reliability

To determine inter-rater reliability, the two trained blinded investigators at each medical center will perform all assessments. To study intra-rater (test-retest) reliability, measures will be carried out by the subject (for the patient-reported severity outcome) and by the same two physicians (for the disease scores) at both screening and baseline visits, which will be separated by 3-4 weeks to minimize recall bias. Intra-rater and inter-rater reliability will be assessed by the intraclass correlation (ICC) for agreement (Shrout and Fleiss, 1979) and will be calculated within the linear mixed-effects model framework (Eldridge et al, 2009). The ICC for the inter-rater agreement will be calculated in the random coefficient model with covariates center and random intercepts for the patient and the physician. Bland-Altman plots will also be used to study patterns of agreements. As per Cicchetti (Cicchetti et al, 1994), interpretation for kappa or ICC for inter-rater agreement measures will be as follows: poor <0.40; fair 0.40-0.59; good 0.60-0.74; excellent 0.75-1.00.

10. ETHICAL CONSIDERATIONS.

10.1. Informed Consent

This clinical study was designed and shall be implemented and reported in accordance with the ICH Harmonized Tripartite Guidelines for Good Clinical Practice, and with the ethical principles laid down in the Declaration of Helsinki.

10.2. Consent Forms

Prior to study entry, a written informed consent must be obtained from the subject (≥ 18 years old). A copy of the subject's signed consent form must be retained in the study file. Documentation of consent process will be placed in source document for each study subject.

10.3. Responsibilities of the Investigator and IRB

A periodic review will be submitted to the IRB at least once per year. The IRB will be notified of completion of the study. After study completion or termination, a final report will be provided to the IRB to close the study. The investigator will maintain an accurate and complete record of all submissions made to the IRB, including a list of all reports and documents submitted. Serious Adverse Events that are reported to Novartis will be submitted promptly to the IRB per IRB guidelines.

At least once per year, the IRB will review and give written approval in order to continue the study. This trial will be conducted in accordance with Good Clinical Practices and the Declaration of Helsinki.

10.4. Publication of Study Protocol and Results

Product: Secukinumab

Protocol Number: CAIN457AUS05T

Date: 14 July 2018

37

The Principal Investigator and co-investigators may publish the results of this study in conjunction with appropriate scientific and medical personnel of either institution. Information obtained from this study may be used for teaching, research, publications, or presentations at scientific meetings. If individual results are discussed, subject identities will be protected by using a subject number rather than name or other identifying information.

11. PROTOCOL ADHERENCE

This protocol defines the study objectives, the study procedures and the data to be collected on study participants. Additional assessments required to ensure safety of subjects should be administered as deemed necessary on a case by case basis. Under no circumstances should an investigator collect additional data or conduct any additional procedures for any research related purpose involving any investigational drugs.

Investigators ascertain they will apply due diligence to avoid protocol deviations. If an investigator feels a protocol deviation would improve the conduct of the study this must be considered a protocol amendment, and unless such an amendment is agreed upon by Novartis and approved by the IRB/IEC and health authorities, where required, it cannot be implemented. All significant protocol deviations will be recorded and reported.

11.1. Protocol Amendments

All changes must be submitted to the IRB. Protocol modifications that impact subject safety or the validity of the study must be approved by the IRB and Novartis Medical Affairs before initiation.

Appendix 1: Schedule of Assessments Flowchart

Phase 1 (double-blind): Visits 1-5;

Crossover: Visit 6

Open label: Visits 7-12

Visit Number	1	2	3	4	5	6	7	8	9	10	11	12
						COW1	OLW1	OLW4	OLW12	OLW20	OLW28	OLW32
	Screen (28 d-21 d of Day 0)	Baseline/ Day 0	Wk 4	Wk 8	Wk 12	Wk 16	Wk 20	Wk 24	Wk 32	Wk 40	Wk 48	Wk 52
Visit Window			±3 days	±3 days	±1 wk	±3 days	±3 days	±1 wk	±1 wk	±1 wk	±1 wk	±1 wk
Consent	X											
Demographics	X											
Inclusion/Exclusion	X	X										
Medical History	X	X	X	X	X	X	X	X	X	X	X	X
Concomitant Meds	X	X	X	X	X	X	X	X	X	X	X	X
AE Assessment	X	X	X	X	X	X	X	X	X	X	X	X
Physical Examination	X	X				X			X			X
Full Skin Examination		X	X	X	X	X	X	X	X	X	X	X
Vital Signs (incl. weight)	X	X	X	X	X	X	X	X	X	X	X	X
Height	X											
Waist circumference		X				X			X			X
Randomization		X										
Saliva Genotyping (if unknown) ²	X											
Buccal swab	X											
Blood Biomarkers	X ¹	X		X		X			X			X
PAX RNA	X ¹	X		X		X			X			X
QuantiFERON®-TB gold	X											X
Hep B/C, HIV testing	X											
Urine HCG(if applicable)	X											X
Chem-20, CBC	X					X			X			X
Lipid panel, glucose, CRP (fasting)		X				X			X			X
Severity evaluations	X	X	X	X	X	X	X	X	X	X	X	X
TEWL		X	X	X	X	X	X	X	X	X	X	X
Tape Strips		X		X		X			X			X
Itch scores		X	X	X	X	X	X	X	X	X	X	X
DLQI and iQoL-32		X				X			X			X
Skin Biopsy (4.5 mm)		X				X			X			X
Photography	X	X	X	X	X	X	X	X	X	X	X	X
Skin Swabs	X	X	X	X	X	X	X	X	X	X	X	X
Injection & Teaching		X										
Dispense study treatment		X	X	X	X	X	X	X	X	X	X	
Review Subject Diary			X	X	X	X	X	X	X	X	X	X

1. To be drawn at screening if the patient is on systemic retinoid
2. At Northwestern only.

Product: Secukinumab

Protocol Number: CAIN457AUS05T

Date: 14 July 2018

All investigators will be trained by [name] before initiation.

Appendix 2: Ichthyosis Area and Severity Index (IASI)

The **IASI** (Ichthyosis **A**rea and **S**everity **I**ndex) is a modification of the global CISI score (see Appendix 2) that incorporates extent through the techniques used for assessment in the EASI and PASI scores for eczema (AD) and psoriasis, respectively. IASI takes only a few minutes to assess and the totals are calculated automatically in spreadsheets. All investigators will be trained by [name] before initiation and with the first few patients using representative examples of different scores in different skin tones and body sites. While this is not a validated score to date, the proposed study is an opportunity to validate this scoring instrument.

The steps for the IASI are as follows:

- a) Determine mean **INTENSITY** of erythema or scaling in a body region (A1 = head and neck; A2 = upper limbs; A3 = trunk; A4 = lower limbs) through either selecting a representative area of ichthyosis or averaging the intensity within a body region. The intensity of redness/ erythema and scaling of the ichthyosis is assessed as none (0), mild (1), moderate (2), severe (3) or very severe (4).

0	None
1	Mild
2	Moderate
3	Severe
4	Very Severe

- b) Determine what percentage of **AREA** within a body region is affected by ichthyosis. In each region, the area is expressed as nil (0), 1-9% (1), 13-29% (2), 30-49% (3), 50-69% (4), 70-89% (5) or 90-100% (6). Many with ichthyosis have generalized involvement with 100% of area affected (e.g., score of 6), but it is possible that areas may be spared (e.g., palms or soles). The mean intensity score (A1-A4 for each site) is multiplied by the number correlating with the percentage within a region with ichthyosis (B1-4).

% involvement	0	1-9%	10 - 29%	30 - 49%	50 - 69%	70 - 89%	90 - 100%
Region score	0	1	2	3	4	5	6

- c) Determine **TOTAL EXTENT** by using a multiplier that takes into account the percentage of the total body surface area represented by each body region (C1 = 0.1 for head and neck; C2 = 0.2 for upper limbs; C3 = 0.3 for trunk; C4 = 0.4 for lower limbs).

The **FINAL SCORE** for each intensity measure (IASI-E or IASI-S) is thus the composite of $(A1+B1) \times C1 + (A2+B2) \times C2 + (A3+B3) \times C3 + (A4+B4) \times C4$.

The **composite score** IASI (max potential 48) = IASI-E (max potential = 24) + IASI-S (max potential = 24).

Product: Secukinumab

Protocol Number: CAIN457AUS05T

Date: 14 July 2018

43

Body region	Erythema (0-4)	Scaling (0-4)	Region score (0-6)	Multiplier	Score per body region
Head/neck	(+))	X	X 0.1	
Trunk	(+))	X	X 0.3	
Upper extremities	(+))	X	X 0.2	
Lower extremities	(+))	X	X 0.4	

TOTAL(Sum Score per Region):

Product: Secukinumab

Protocol Number: CAIN457AUS05T

Date: 14 July 2018

Appendix 3: Congenital Ichthyosis Severity Score (CISI): *To be performed by Investigators and by Subject

Ichthyosis Likert Scales for Grading of Clinical Severity

1. Please indicate your level of skin scale, as it appears today:

	 ₁ No scale	 ₂ Minimal scale	 ₃ Some Scale	 ₄ Moderate Scale	 ₅ Severe Scale
X-linked ichthyosis					
Lamellar ichthyosis					
Epidermolytic hyperkeratosis					
Netherton syndrome					

2. Please indicate your level of redness, as it appears today:

 ₁ No red coloration	 ₂ Faint red coloration	 ₃ Light red coloration	 ₄ Moderate red coloration	 ₅ Bright red coloration	 ₆ Dusky red coloration

3. Please indicate your level of hair loss, as it appears today:

- ₁ Normal hair ₂ Mild (<25% hair loss) ₃ Moderate (25-75%) hair loss ₄ Severe (>75%) hair loss ₅ No hair

Product: Secukinumab

[figure not shown]

Protocol Number: CAIN457AUS05T

Date: 14 July 2018

[figure not shown]

45

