Index. CISI is a validated score that assesses individual scores for erythema, scaling and alopecia, but is limited in that it is not a single score, includes a feature found in the minority of patients (alopecia) and includes non-uniform Likert scales (0-4+ or 0-5+). M-CISI eliminates the alopecia score, adopts a 5-point Likert for erythema and scaling, and averages the erythema and scaling scores for a single global assessment; it is a new scale that is being validated herein but will not be used for endpoints. IASI is a composite score based on the global CISI score that captures differences in severity in different body regions as a function of their body surface area and also standardizes the number of choices within the Likert scales for erythema and scaling. As in the EASI score for AD and the PASI score for psoriasis, IASI evaluates erythema and scaling as 0-4+ in severity at each of 4 locations: head and neck (including scalp); arms (including palms); legs (including soles); and trunk, prorated based on body surface area in these sites and the percentage of involvement in each of these sites (total possible score for each is 24 and total composite score is 48). To include a patient-reported severity score, we will use the Congenital Ichthyosis Severity Index, which has been validated for patient use (Kamalpour et al 2010), and the m-CISI. We will also pilot in the US a complex, non-validated burden of disease scoring system proposed by Bodemer et al in France, which heavily weighs associated morbidity (contractures, ectropion, mouth tightness, fissures) in addition to other measures of severity. All investigators/ sub-investigators will be trained based on photographs before study initiation to uniformly assign CISI, m-CISI, Bodemer, and IASI scores. A huge issue is the paucity of validated scores for ichthyosis severity. Our evaluations will be performed concurrently (but without conferring) by two investigators to allow inter-rater reliability, as well as at screening and again at baseline (at 3-4 weeks to minimize recall bias) for assessing test-retest reliability. As such, we hope to use this opportunity to assess reliability in these un-validated instruments. Patient-reported itch will be quantified on a 0-10 numerical rating scale (NRS) and by 5-D itch score (Elman et al 2009); a 1-10 score pain assessment is part of the Bodemer scale. The Yale Severity Index was recently developed and tested at a recent meeting of the Foundation for Ichthyosis and Related Skin Types. It includes a 0-4+ scale for erythema and for scaling, and provides pictorial representations for comparison, dividing scaling into lamellar and keratoderma scale scores. This study is the first time it will be applied to patients in an investigation.

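### Appendix 2 prints an additive formula for IASI-E and IASI-S where its own step b, score sheet and stated maxima require multiplication

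*Combined protocol and SAP*

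**What the plan says.** Appendix 2 builds the IASI in steps. Intensity of erythema or scaling is rated 0 to 4 in each of four body regions (A1 to A4). The share of each region affected is scored 0 to 6 (B1 to B4). Step b then combines them: "The mean intensity score (A1-A4 for each site) is multiplied by the number correlating with the percentage within a region with ichthyosis (B1-4". Step c weights the regions by 0.1, 0.2, 0.3 and 0.4 (C1 to C4).

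The final-score line combines them differently. The score "for each intensity measure (IASI-E or IASI-S) is thus the composite of $(A1+B1", with the same bracket repeated for regions 2 to 4, each multiplied by its weight. The next line gives the ceilings: "IASI (max potential 48) = IASI-E (max potential = 24) + IASI-S (max potential = 24". Section 6.1.9 repeats 24 and 48 and describes the score as "prorated based on body surface area in these sites and the percentage of involvement in each of these sites".

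The score sheet that follows has columns for erythema, scaling, "Region score (0-6" and the multiplier, and ends in "TOTAL(Sum Score per Region". It sets out the composite only; there is no sheet for either subscore. The introduction to Appendix 2 adds that "the totals are calculated automatically in spreadsheets".

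There is also a smaller mismatch. The step b text says "the area is expressed as nil (0), 1-9% (1), 13-29% (2), 30-49% (3", while the table directly beneath starts area score 2 at 10%.

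**The concern.** Appendix 2 holds two rules for the same subscore, and they give different numbers. IASI-E of 12 is an inclusion criterion (Section 4.1 and the synopsis). IASI-E and IASI-S are secondary efficacy endpoints, both as reductions and as 50% and 75% responder outcomes (Section 2.1). The only equation written for them is the additive one.

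The additive rule is not a simple rescaling of the multiplicative one. It leaves a floor set by area alone, so percentage reductions shrink and responder thresholds change meaning. It also breaks the identity that the composite equals IASI-E plus IASI-S. Appendix 2 says the IASI has not yet been validated and presents this trial as a chance to do so, which makes a correct written definition more important.

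**Working it through.** **Inputs (Appendix 2 unless noted).** Intensity A: 0 to 4. Area score B: 0 to 6. Weights C: 0.1 + 0.2 + 0.3 + 0.4 = 1.0. Stated maxima: 24, 24 and 48. Entry criterion: IASI-E of 12, described as at least moderate erythema (Section 4.1). Planning cohort: mean composite 28.9 (Section 9.5).

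**1. Reproduce the stated maxima with step b.** Subscore = sum of (A × B) × C. At the top of both scales this is 4 × 6 × 1.0 = 24 per subscore and 24 + 24 = 48 composite. Both match.

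**2. Apply the final-score line as printed.** Subscore = sum of (A + B) × C. At the top of both scales this is (4 + 6) × 1.0 = 10 per subscore and 20 composite. Neither matches. These maxima need no assumption about the patients.

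**3. Check against the score sheet.** Read as (erythema + scaling) × region score × multiplier, its maximum is (4 + 4) × 6 × 1.0 = 48. The plus sign on the sheet joins erythema and scaling, not intensity and area, so it does not support the printed line.

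**4. Compare the rules on the same ratings.** Assume the same intensity, and an area score of 6, in all four regions:

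| Erythema / scaling | Score sheet | IASI-E + IASI-S, multiplied | IASI-E + IASI-S, as printed |
|---|---|---|---|
| Very severe / very severe (4, 4) | 8 × 6 = 48 | 24 + 24 = 48 | 10 + 10 = 20 |
| Severe / moderate (3, 2) | 5 × 6 = 30 | 18 + 12 = 30 | 9 + 8 = 17 |
| Moderate / moderate (2, 2) | 4 × 6 = 24 | 12 + 12 = 24 | 8 + 8 = 16 |

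Multiplied subscores agree with the sheet in every row. Printed subscores agree in none.

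**5. Check against the entry criterion.** At area score 6, an IASI-E of 12 means intensity 12 / 6 = 2 by multiplication, which is moderate, as Section 4.1 describes it. By the printed line it means intensity 12 − 6 = 6, on a scale that stops at 4.

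**6. Check against the planning cohort.** The mean of 28.9 exceeds the printed ceiling by 28.9 − 20 = 8.9 points, so those scores cannot have come from the printed line.

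**7. Effect on responder outcomes if the line were used.** With area held at 6, full clearance of very severe erythema takes IASI-E from 10 to 6, a reduction of 4 / 10 = 40%. A 50% response could not be reached by a change in intensity alone. By multiplication the same change is 24 to 0, or 100%.

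**8. Area bands.** In the step b text, score 1 ends at 9% and score 2 begins at 13%, so involvement of 10 to 12% has no score. The table gives it 2.

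**The case against.** The strongest reply is that the appendix resolves the matter itself. Steps a to c give a complete and correct rule in words immediately above the faulty line, and the stated maxima immediately below it confirm multiplication. Investigators are to be trained and totals come from a spreadsheet, so hand calculation from this line is not the planned procedure. Anyone who did apply it could enrol nobody, and would notice at the first screening. Nothing in the protocol shows that the spreadsheet uses the printed line, and the cohort mean indicates that earlier scoring did not.

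All of that stands. It limits the finding to an incorrect written definition, with no demonstrated effect on data, eligibility or power. It does not make the line right. The spreadsheet formula is not shown, so the protocol gives no direct assurance about what will be computed.

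A second reply is that the text was read by machine. A repeated misreading of one symbol cannot be fully excluded without the PDF. However, the plus sign appears in all four brackets, while the multiplication signs in the same line came through correctly, so this is unlikely. The caution has more force for the 13% in step b, which is a single occurrence and could be a misread digit. That point also matters little in practice, because Section 3.5 describes these patients as having total body involvement. The score sheet is itself imperfectly extracted, and reading it as a product is an inference, although that reading reproduces 48 exactly.

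**Conclusion.** The concern holds. As printed, the final-score line caps each subscore at 10 and the composite at 20, against the stated 24 and 48. Step b, the stated maxima, the score sheet, the IASI-E criterion of 12 and the cohort mean of 28.9 fit multiplication and not the printed line.

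The error is contained. The primary endpoint, change in composite IASI at week 16, is not left undefined, and the sample size calculation is unaffected. What is wrong is the only written equation for IASI-E and IASI-S. It should be corrected, but it does not threaten the design. The maxima rest on the printed scales and weights alone. The worked comparisons assume uniform intensity and an area score of 6 in every region. The effect on actual scoring is unknown, because the spreadsheet formula is not given.

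**What to change.** Replace the final-score line, for each subscore, with (A1 × B1) × C1 + (A2 × B2) × C2 + (A3 × B3) × C3 + (A4 × B4) × C4. Reconcile the lower limit of area score 2 between the step b text and the table, after checking the source file.

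Then confirm that the scoring spreadsheet returns, for IASI-E / IASI-S / composite with 90–100% area in all regions:

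- 24 / 24 / 48 for very severe erythema and scaling;
- 12 / 12 / 24 for moderate erythema and scaling;
- 18 / 12 / 30 for severe erythema with moderate scaling, with the subscores summing to the score-sheet total.

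The cost is a one-line correction, one area band and three test cases. It needs no added patients, visits or data.

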Appendix 4: Modified CISI (m-CISI): *To be performed by Investigators and by Subject

1. Please indicate your level of skin scale, as it appears today:

0: No scale	1: Minimal Scale	2: Moderate Scale	3: Severe Scale	4: Very Severe Scale
Lamellar ichthyosis				
Epidermolytic hyperkeratosis				
Netherton syndrome				
CIE				

2. Please indicate your level of skin redness, as it appears today:

				
0: No red coloration	1: Light red coloration	2: Moderate red coloration	3: Bright red coloration	4: Dusky Red Coloration

TOTAL(scale +erythema scores):

Appendix 5: Bodemer Scale

Product: Secukinumab
 Protocol Number: CAIN457AUS05T
 Date: 14 July 2018

(a) BODY SURFACE AREA WITH SCALES **(b) BODY SURFACE AREA WITH ERYTHEMA**

EXTENT: A =%

EXTENT: B =%

(c) PRURITUS: (C) (Value in cm)

PRURITUS (0 – 10) 0 _____ 10
 VISUAL ANALOGUE SCALE (average for the last 3 last days and nights)

(d) SKIN PAIN: (D) (Value in cm)

SKIN PAIN (0 – 10) 0 _____ 10
 VISUAL ANALOGUE SCALE (average for the last 3 last days and nights)

(e) SEVERITY OF 10 SYMPTOMS: (E) (Cumulated severity score for 10 symptoms: total value ranging from 0 to 60)

SCORE = A/10 + B/10 + C + D + E = / 100

10 SYMPTOMS	

Scale grade: body
 
0: absent 1: light (thin scales) 3: moderate (visible scales) 6: severe (thick scales)
	
Retraction: hand
 
0: absent 1: at least two fingers of one hand 3: all the fingers of one hand 6: both hands

Scale grade: scalp
 
0: absent 1: light (thin scales) 3: moderate (visible scales) 6: severe (thick scales)
	
Retraction: foot
 
0: absent 1: at least two toes of one foot 3: all the toes of one foot 6: both feet

Palmoplantar keratoderma (PPK)
 
0: absent 1: light (not very pronounced) 3: moderate (obvious) 6: severe (with fissures)
	
Functional impairment
 
0: absent 1: neck (rotation, ante/retroflexion) 3: shoulders with 'winding' = 'inward' shoulders 6: limb (s), whatever the location

Erythema (on the most representative area)
 
0: absent 1: light 3: moderate 6: severe
	
Eyelids
 
0: no ectropion 1: ectropion of one eyelid 3: lack of eye occlusion: persistent slit opening 6: lack of eye occlusion: persistent opening > slit

Fissures (apart from PPK)
 
0: absent 1: present, painless (one site only) 3: present, painless (several sites) 6: present, painful (one or several sites)
	
Mouth (notwithstanding fissures at commissures)
 
0: no repercussion 1: mild eclabium 3: characterised eclabium 6: limited opening of the mouth (measurement of the maximal opening from upper lip to lower lip in cm)

